- Chronic kidney disease: inpatients with at least once 1 discharged diagnosis CKD (ICD-10 N18), or inpatients with the last estimated glomerular filtration rate (eGFR, calculated by CKD-EPI equation) <60 mL/min/1.73 m^2 or prescription of dialysis, but not with the diagnosis of acute kidney injury (ICD-10 N17); or outpatients with at least 2 diagnosis of CKD (the first diagnosis will be the index diagnosis, and the time interval between diagnoses is not restricted) or with two consecutive eGFR (calculated by CKD-EPI equation) <60 mL/min/1.73 m^2 by 90 days or more.
- High cardiovascular risk: patients with at least 1 discharged diagnosis or 2 outpatient diagnosis of hypertension (the first diagnosis will be the index diagnosis, and the time interval between diagnoses is not restricted) (ICD-10 I10-I15); or at least 1 discharged diagnosis or 2 outpatient diagnosis of hyperlipidemia (ICD-10 E78.001-E78.003, E78.101, E78.203, E78.301-E78.304, E78.306, E78.401, E78.501, E78.902)

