**9.3.2.1 Primary outcomes**

1. The proportion of diabetic/non-diabetic patients with established cardiovascular disease, or chronic kidney disease, or at high cardiovascular risk.
2. The proportion of diabetic patients with established cardiovascular disease, or chronic kidney disease, or at high cardiovascular risk among all diabetic patients.
3. The proportion of non-diabetic patients with established cardiovascular disease, or chronic kidney disease, or at high cardiovascular risk among all non-diabetic patients.

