### **9.7.1 Main analysis**

Before analyses start, 200 randomly selected medical chart will be fully reviewed by well-trained experts to validate the accuracy and sensibility of code used to identify patients with cardiovascular disease or at high cardiovascular risk, chronic kidney disease and type 2 diabetes. This QC procedure for database study would be performed by [REDACTED].

The analyses will mainly describe the patient demographic characteristics, comorbidities, treatment pattern and economic burden based on 40 hospitals EMRs of Tianjin regional database. Descriptive data will be provided. The statistical methods and analyses will be described in detail in a Statistical and Epidemiological Analysis Plan (SEAP) prior to the commencement of any analyses.

Characteristics presented as continuous data will be summarized through means, standard deviations, medians, minimum and maximum values, whereas, categorical data will be summarized as counts and proportions.

All tests will be two-sided unless otherwise specified

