### **9.9 LIMITATIONS OF THE RESEARCH METHODS**

There is no unique ICD code for cardiovascular disease, CKD or at high cardiovascular risk. Each of those diseases has more than one ICD code in the medical charts. The subjects came from different hospitals; the understanding of ICD code may be different according to different hospitals.

The study is limited in representativeness and generalizability. Of 600,000 patients, only 100,000 patients contained comprehensive information about patients' basic information, medical advice, diagnosis, laboratory examination, medical records and medical costs.

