9.3.1 Exposure? (e.g. WHO Drug Dictionary, Anatomical Therapeutic Chemical (ATC) Classification System)				

Section 9: Data sources	Yes	No	N/A	Section Number
9.3.2 Outcomes? (e.g. International Classification of Diseases (ICD), Medical Dictionary for Regulatory Activities (MedDRA))				
9.3.3 Covariates and other characteristics?				
9.4 Is a linkage method between data sources described? (e.g. based on a unique identifier or other)				9.4

Comments:

--

Section 10: Analysis plan	Yes	No	N/A	Section Number
10.1 Are the statistical methods and the reason for their choice described?				9.7.1
10.2 Is study size and/or statistical precision estimated?				9.5
10.3 Are descriptive analyses included?				9.7.1
10.4 Are stratified analyses included?				
10.5 Does the plan describe methods for analytic control of confounding?				
10.6 Does the plan describe methods for analytic control of outcome misclassification?				
10.7 Does the plan describe methods for handling missing data?				
10.8 Are relevant sensitivity analyses described?				9.7.1

Comments:

--

Section 11: Data management and quality control	Yes	No	N/A	Section Number

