7.2.1 Primary outcomes

- 1) The proportion of diabetic/non-diabetic patients with established cardiovascular disease, chronic kidney disease, or at high cardiovascular risk.
- 2) The proportion of diabetic patients with established cardiovascular disease, chronic kidney disease, or at high cardiovascular risk among all patients with diabetes;
- 3) The proportion of non-diabetic patients with established cardiovascular disease, chronic kidney disease, or at high cardiovascular risk among patients without diabetes;

Table 1. The proportion of patients with disease or risk among diabetic or non-diabetic patients

| | 2015 | | 2016 | | ... | | 2019 | | Overall | |
|--|-----------------|----------------|-----------------|----------------|-----------------|----------------|-----------------|----------------|-----------------|----------------|
| | Outpatie nts | Inpatient s | Outpatie nts | Inpatie nts | Outpatie nts | Inpatient s | Outpatie nts | Inpatient s | Outpatie nts | Inpatient s |
| | n (%) | n (%) |
| Patients diagnosed with diabetes | | | | | | | | | | |
| Group A (n, %) | | | | | | | | | | |
| with cardiovascular disease | | | | | | | | | | |
| with chronic kidney disease | | | | | | | | | | |
| at high cardiovascular risk | | | | | | | | | | |
| Patients diagnosed without diabetes | | | | | | | | | | |
| Group C (n, %) | | | | | | | | | | |
| with cardiovascular disease | | | | | | | | | | |
| with chronic kidney disease | | | | | | | | | | |
| at high cardiovascular risk | | | | | | | | | | |

Note: Group A: Diabetes with cardiovascular disease, chronic kidney disease or at high cardiovascular risk; Group B: Diabetes without cardiovascular disease, chronic kidney disease or at high cardiovascular risk; Group C: Non-diabetes with cardiovascular disease, chronic kidney disease or at high cardiovascular risk; Group D: Non-diabetes without cardiovascular disease, chronic kidney disease or at high cardiovascular risk;

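### CKD is classified by different rules for inpatients and outpatients, so part of any difference between the two CKD columns in SAP Table 1 can come from the rule, in a direction and size the documents do not determine

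*Protocol*

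**What the plan says.** Protocol 9.2.2, repeated in SAP 6.3, gives these routes to CKD:

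- **Inpatients:** one N18 discharge diagnosis; or "inpatients with the last estimated glomerular filtration rate" below 60 mL/min/1.73 m²; "or prescription of dialysis, but not with the diagnosis of acute kidney injury (ICD-10 N17"). The sentence does not make clear whether the N17 exception covers the eGFR route, the dialysis route or both.
- **Outpatients:** at least two CKD diagnoses, "or with two consecutive eGFR (calculated by CKD-EPI equation") below 60, separated by 90 days or more. The pair is not restricted to the last two tests. Dialysis is not listed.

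The main table for the primary outcomes, SAP Table 1 ("The proportion of patients with disease or risk among diabetic or non-diabetic patients"), has outpatient and inpatient columns next to each other for each year and overall, with a CKD row under Group A and another under Group C. It does not split CKD by route. Primary outcome 2 in Protocol 9.3.2.1 is worded as "The proportion of diabetic patients with established cardiovascular disease, or chronic kidney disease, or at high cardiovascular risk among all diabetic patients", and outcome 3 is its non-diabetic counterpart.

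On checks, Protocol 9.7.1 plans a review of 200 charts to validate the identifying codes and names CKD. SAP 11 describes the same review without naming CKD, and adds a check that 1000 extracted records meet the criteria. Checklist item 10.8 in Protocol Annex 2 ("Are relevant sensitivity analyses described") is answered yes with a pointer to 9.7.1. Item 10.6, on control of outcome misclassification, is answered no.

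**The concern.** By asking outpatients for 90 days of persistence, the plan treats persistence as part of CKD. It drops that requirement for an inpatient with a low last value. A single value below 60 can reflect measurement variation or a temporary fall during the illness that led to admission. The N17 exception removes such a fall only where acute kidney injury was coded.

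A reader who sees different CKD percentages in adjacent columns will tend to read a difference in disease. With the plan followed exactly, that reader cannot tell how much of the inpatient figure rests on one unconfirmed eGFR, or how much of a gap comes from the definition. CKD is one of three named conditions in the main table for the primary outcomes. The effect falls mainly on the CKD rows: a patient moves from Group B to A, or from D to C, only if there is no cardiovascular disease, heart failure, hypertension or hyperlipidaemia to qualify them already.

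**Working it through.** **1. The rules side by side**

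| Route | Inpatients | Outpatients |
|---|---|---|
| Code | one discharge diagnosis | two diagnoses |
| eGFR below 60 | the last value only | any consecutive pair, 90 days or more apart |
| Dialysis | qualifies | not listed |
| N17 exception | yes, scope unclear | none stated |

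The eGFR rules differ in two ways that pull in opposite directions. Needing two low values makes it harder for an outpatient to qualify. Accepting any consecutive pair gives an outpatient a new chance with every further test, while an inpatient is judged once, on the last value.

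**2. Illustration with equal kidney function in both settings**

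The documents give no eGFR distribution, retest share or test frequency, so every input here is assumed. True eGFR x is normal with mean 82 and SD 18. A measured value is normal around x with SD 8. Tests are independent given x, and outpatient tests are all at least 90 days apart. There are no temporary falls. The chance that one value is below 60 is p(x) = Φ((60 − x)/8).

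- Share with true eGFR below 60: Φ((60 − 82)/18) = 0.111.
- Inpatient rule, one value: E[p] = 0.1320.
- Outpatient rule, exactly two tests: E[p²] = 0.0832.
- Ratio: 0.1320 / 0.0832 = 1.59.

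For k outpatient tests, let q(k) be the chance of no consecutive low pair: q(0) = q(1) = 1 and q(k) = (1 − p)·q(k−1) + p(1 − p)·q(k−2). The outpatient share is E[1 − q(k)].

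| Outpatient tests k | Outpatient share | Inpatient/outpatient ratio |
|---|---|---|
| 2 | 0.0832 | 1.59 |
| 4 | 0.1207 | 1.09 |
| 5 | 0.1328 | 0.99 |
| 6 | 0.1430 | 0.92 |
| 8 | 0.1583 | 0.83 |
| 12 | 0.1790 | 0.74 |

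The ratio crosses 1 at about five tests.

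**3. What raises the ratio**

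- *Incomplete retesting.* If a share s of outpatients is retested, the ratio is divided by s. With two tests, s = 0.6 gives 0.1320 / (0.6 × 0.0832) = 2.64, and s = 0.3 gives 5.29. With twelve tests, s = 0.6 gives 0.1320 / (0.6 × 0.1790) = 1.23.
- *Uncoded falls in inpatients.* If 10% or 20% of inpatients have an uncoded 10-unit fall, the inpatient share becomes 0.146 or 0.160. The two-test ratio is then 1.75 or 1.92.

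**4. Unconfirmed single values**

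In the base case, the share of single low values that a second stable value would not confirm is 1 − 0.0832/0.1320 = 0.37. Varying the mean over 75 to 90, the SD over 15 to 22 and the within-person SD over 5 to 10, with uncoded falls in 0 to 20% of inpatients, gives 16% to 68%. Unconfirmed does not mean free of CKD, because some patients with a true value below 60 also have a second reading above it.

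**5. Whether the planned checks reach this**

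- The 200-chart review tests codes. It mentions neither the eGFR route nor a split by setting.
- The 1000-record check asks whether the criteria were applied, not whether a low value was chronic.
- Protocol 9.7.1, to which checklist item 10.8 points, says "The analyses will mainly describe the patient demographic characteristics, comorbidities, treatment pattern and economic burden" and contains no sensitivity analysis.
- Protocol 9.9 notes that "the understanding of ICD code may be different according to different hospitals", which concerns coding and not this rule.

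**6. Still open**

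The documents do not say whether a year column uses only that year's tests, or whether a patient seen in both settings carries CKD status into both columns. Each would change the size of the effect.

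**The case against.** The strongest case for the plan is that a rule per setting is practical, because many inpatients may have no repeat test. The rule is fully written out in both documents, and coded acute kidney injury is excepted. No objective compares inpatients with outpatients, and SAP 10.1 does not name setting among its test subgroups. Reporting the settings separately exposes the difference rather than hiding it in a pooled figure. The 200-chart review does name CKD in the protocol.

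Most of this stands, and it is why the definition should not be replaced. It does not make the adjacent columns comparable, and it does not show how many inpatients qualify on one value alone.

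Three stronger readings are tempting, and the documents support none of them:

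- *That the rule inflates inpatient CKD relative to outpatient CKD.* This holds in the illustration with exactly two outpatient tests. With all outpatients retested it reverses from about five tests on. Test frequency is not in the documents.
- *That the overall primary proportions are distorted by a known amount.* Outcomes 2 and 3 would mix both standards if a combined figure were reported, but the Table 1 shell prints none.
- *That the plan has no sensitivity analysis at all.* None is visible, but the text available does not show Protocol 9.7.2 or SAP 10.2. The claim is limited to what can be read.

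A fair objection also applies to the remedy. Under a common two-test rule with equal kidney function, the ratio between settings equals the ratio of retested shares: 30% of inpatients against 60% of outpatients would give 0.5. Such an analysis partly measures testing frequency and must be labelled so.

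**Conclusion.** The point holds in limited form. CKD is classified by different laboratory, code and dialysis routes in the two settings. SAP Table 1 sets the results side by side, and nothing in the visible text measures what the rule contributes. Part of any inpatient/outpatient CKD difference can therefore be produced by the definition, and some inpatient CKD rests on a single unconfirmed value.

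Neither direction nor size can be derived from the documents. The ratios of 1.59, about 1.0 and 0.74 for two, five and twelve outpatient tests show only that the answer depends on unreported quantities: test frequency, retest share, within-person variation and uncoded falls. The consequence is mainly for interpreting the CKD rows. It does not undermine the study, and the change is a worthwhile low-cost improvement to settle before analysis.

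**What to change.** Keep the current definition as the main analysis, and make these changes:

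1. In SAP Table 1, split the CKD rows under Groups A and C by qualifying route (N18 code, dialysis, eGFR only) in each setting. Label inpatients who qualify only on a single eGFR as 'reduced eGFR, chronicity unconfirmed'.
2. As a sensitivity analysis, repeat the CKD rows with the same two-value, 90-day laboratory rule in both settings.
3. Print, for each column, the number of patients with two eGFR values at least 90 days apart. This requires stating which test dates feed each year column.
4. State that the sensitivity analysis also reflects testing frequency and is neither a corrected value nor a bound.
5. Add to Protocol 9.9 that CKD figures are not directly comparable between settings because the laboratory, code and dialysis routes differ.

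Separately, and minor: reconcile the disease list of the 200-chart review between Protocol 9.7.1 and SAP 11.

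The cost is a few table rows, one repeated set of proportions, one count per column and short wording. Creatinine, eGFR and test dates are already among the variables in Protocol 9.3. The drawback is that the sensitivity figures miss true CKD in patients tested only once, which is why the counts belong beside them.

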#### **Inclusion Criteria:**

- 1) Patients in the Tianjin regional database from 01/01/2015 to 31/12/2019.
- 2) Group A: patients with diagnosis of diabetes, and with diagnosis of cardiovascular disease, heart failure, chronic kidney disease or at high cardiovascular risk.
- 3) Group B: patients with diagnosis of diabetes, but not with diagnosis of cardiovascular disease, heart failure, chronic kidney disease or at high cardiovascular risk.
- 4) Group C: patients with diagnosis of cardiovascular disease, heart failure, chronic kidney disease or at high cardiovascular risk, but not with diagnosis of diabetes.
- 5) Group D: patients without diagnosis of cardiovascular disease, heart failure, chronic kidney disease or at high cardiovascular risk, and without diagnosis of diabetes. We will randomly select a group of non-diabetic patients without any of the above diseases by matching on age and gender.

Definition of diabetes, cardiovascular disease, chronic kidney disease and high cardiovascular risk:

- Diabetes: patients with at least 1 discharged diagnosis or 2 outpatient diagnosis of diabetes (the first diagnosis will be the index diagnosis, and the time interval between diagnoses is not restricted) (International classification of disease (ICD)-10 E10-E14)
- Cardiovascular disease: patients with at least 1 discharged diagnosis or 2 outpatient diagnosis of ischemic heart diseases (the first diagnosis will be the index diagnosis, and the time interval between diagnoses is not restricted) (ICD-10 I20~I25); or patients with at least 1 discharged diagnosis or 2 outpatient diagnosis of cerebrovascular diseases (the first diagnosis will be the index diagnosis, and the time interval between diagnoses is not restricted) (ICD-10 I60~I69); or patients with at least 1 discharged diagnosis or 2 outpatient diagnosis of ischemic peripheral artery disease (the first diagnosis will be the index diagnosis, and the time interval between diagnoses is not restricted) (ICD-10 E10.501, E11.603, E14.501, E14.606, E14.503, I73.9, I99.03, I99.04);

- Heart failure: patients with at least 1 discharged diagnosis or 2 outpatient diagnosis of heart failure (the first diagnosis will be the index diagnosis, and the time interval between diagnoses is not restricted) (ICD-10 I50).

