**9.3.1 Exposures**

Not applicable.

We defined four groups (group A-D) according to the diagnosis and laboratory measurements. The group A and group B included all diabetic patients with/without established CV disease, CKD, or at high CV risk, respectively. The group C included all non-diabetic patients with established cardiovascular disease, chronic kidney disease, or at high cardiovascular risk. The group D included non-diabetic patients without established cardiovascular disease, chronic kidney disease, and not at high cardiovascular risk. For group D, we will randomly sample study populations to acquire a 1:1 sample of non-diabetic patients without disease by matching on age and gender with group A.

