**9.3.2.2 Secondary outcomes**

1. The demographic characteristics of the latest visit for all patients, as well as the trends for inpatients over time (2015, 2017, and 2019 respectively):
  - 1) Age at admission
  - 2) Gender
  - 3) Insurance payment
2. The clinical characteristics of the studied population of the latest visit for all patients, as well as the trends for inpatients over time (2015, 2017, and 2019 respectively):
  - 1) Discharge department
  - 2) Death
  - 3) Laboratory test results:
    - a) HbA1c
    - b) random blood glucose
    - c) serum creatine

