7.2.2 Secondary outcomes

- 1) The demographic characteristics of the latest visit for all patients, as well as the trends for inpatients over time (2015, 2017, and 2019 respectively). Clinical characteristics of outpatients and hospitalized patients will be described respectively.

Table 2. The demographic and clinical characteristics of the latest visit

| Outpatients | | | | Inpatients | | | | Total patients |
|--|----------------|----------------|----------------|-------------------|----------------|----------------|----------------|-----------------------|
| Group A | Group B | Group C | Group D | Group A | Group B | Group C | Group D | |
| Demographic characteristics in 2015 | | | | | | | | |
| Age (mean, sd) | | | | | | | | |
| Gender (n, %) | | | | | | | | |
| Insurance payment (n, %) | | | | | | | | |
| Demographic characteristics in 2017 | | | | | | | | |
| Age (mean, sd) | | | | | | | | |
| Gender (n, %) | | | | | | | | |
| Insurance payment (n, %) | | | | | | | | |
| Demographic characteristics in 2019 | | | | | | | | |
| Age (mean, sd) | | | | | | | | |
| Gender (n, %) | | | | | | | | |
| Insurance payment (n, %) | | | | | | | | |

Note Group A Diabetes with cardiovascular disease, chronic kidney disease or at high cardiovascular risk; Group B Diabetes without cardiovascular disease, chronic kidney disease or at high cardiovascular risk; Group C Non-diabetes with cardiovascular disease, chronic kidney disease or at high cardiovascular risk; Group D Non-diabetes without cardiovascular disease, chronic kidney disease or at high cardiovascular risk;

2) The clinical characteristics of the studied population of the latest visit for all patients, as well as the trends for inpatients over time (2015, 2017, and 2019 respectively). Clinical characteristics of outpatients and hospitalized patients will be described respectively.

Table 3. The clinical characteristics of the latest visit

| Outpatients | | | | Inpatients | | | | Total patients |
|---|----------------|----------------|----------------|-------------------|----------------|----------------|----------------|-----------------------|
| Group A | Group B | Group C | Group D | Group A | Group B | Group C | Group D | |
| Clinical characteristics in 2015 | | | | | | | | |
| Department of discharge | | | | | | | | |
| Death | | | | | | | | |
| Clinical characteristics in 2017 | | | | | | | | |
| Department of discharge | | | | | | | | |
| Death | | | | | | | | |

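### For inpatients with no other qualifying disease, a single last eGFR sets the group, so the Death rows of SAP Table 3 are partly shaped by the deaths themselves

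*Protocol*

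**What the plan says.** Protocol 9.2.2 and SAP 6.3 give the same eGFR criterion. Among the ways to be classed as CKD is "inpatients with the last estimated glomerular filtration rate (eGFR, calculated by CKD-EPI equation) <60" (in units of mL/min/1.73 m²). It has no time window, no repeat measurement and no provision for patients who die. Neither document says whether *last* means last in a stay or last in 2015-2019.

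The same definition contains:
- a restriction, "but not with the diagnosis of acute kidney injury (ICD-10 N17", read here as applying to the eGFR and dialysis routes;
- other routes to CKD: an N18 discharge diagnosis, a dialysis prescription, or two outpatient CKD diagnoses;
- a stricter eGFR route for outpatients, "with two consecutive eGFR (calculated by CKD-EPI equation) <60" at least 90 days apart.

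CKD status feeds the grouping. Protocol 9.3.1 states "We defined four groups (group A-D) according to the diagnosis and laboratory measurements", and Protocol 9.2.2 keeps in the diabetic comparator, Group B, only those diabetic patients who are free of CKD and of every other qualifying condition. Group D excludes CKD in the same way and is matched 1:1 to Group A on age and gender.

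Death is listed in Protocol 9.3.2.2 under "The clinical characteristics of the studied population of the latest visit for all patients". In SAP 7.2.2, "Table 3. The clinical characteristics of the latest visit" has a Death row for each of 2015, 2017 and 2019, with Groups A to D as columns. SAP 6.1 presents the four groups as built to be compared.

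**The concern.** A variable that defines the groups should not be a product of the outcome compared across them. In a patient discharged alive, the last eGFR is a value from near discharge. In a patient who dies in hospital, it may be taken during terminal decline, when creatinine can rise whatever the earlier kidney function. A diabetic patient with no chronic disease who dies this way can be counted in Group A instead of B. The non-diabetic counterpart enters Group C and leaves the pool from which D is sampled.

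At stake is how the Death rows are read. A reader could not separate a real difference in mortality from one created by the definition. More data do not dilute an error that depends on the outcome, and matching D to A on age and gender does not remove it.

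**Working it through.** **Does the mechanism follow from the text?** For an in-hospital death the latest visit is the fatal stay. The last eGFR normally comes from that stay on either reading of *last*. CKD alone is enough to move a patient from B to A, or out of the D pool into C. So the grouping value and the outcome can come from the same stay.

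**Does anything else in the plan close the gap?**
- The N17 restriction works only where acute injury was coded, and Protocol 9.9 concedes that hospitals may understand ICD codes differently.
- The 200-chart review (Protocol 9.7.1, SAP 11) checks the codes used to identify patients. The SAP version does not list CKD among the conditions checked.
- The ENCePP checklist (item 10.8) points to Protocol 9.7.1 for sensitivity analyses, but that section describes none.

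**Size.** The documents give no death rate, no A:B split and no share of deaths with a low final eGFR, so there is no planned figure to reproduce. Everything below rests on assumed inputs.

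*Illustration 1.* Take 100 diabetic inpatients, 80 in A and 20 in B, with true death risk 3% in both. Deaths are 80 × 0.03 = 2.4 in A and 20 × 0.03 = 0.6 in B. Let f be the share of Group B decedents reclassified (final eGFR below 60, no N17), with no survivors reclassified.

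- Observed A = (2.4 + 0.6f)/(80 + 0.6f)
- Observed B = 0.6(1 − f)/(20 − 0.6f)

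| f | Observed A | Observed B | Ratio (true 1.00) | Group A share (true 80.00%) |
|---|---|---|---|---|
| 0.2 | 2.52/80.12 = 3.15% | 0.48/19.88 = 2.41% | 1.30 | 80.12% |
| 0.3 | 2.58/80.18 = 3.22% | 0.42/19.82 = 2.12% | 1.52 | 80.18% |
| 0.5 | 2.70/80.30 = 3.36% | 0.30/19.70 = 1.52% | 2.21 | 80.30% |

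With true risks of 5% in A and 3% in B (ratio 1.67), the observed ratio is 2.13 at f = 0.2 and 3.52 at f = 0.5.

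*Illustration 2, letting survivors be reclassified too.* Let w be the share qualifying by other routes, m the common death risk, and g the share of otherwise unaffected survivors reclassified.

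- With disease: [wm + (1 − w)mf] / [w + (1 − w)(mf + (1 − m)g)]
- Without disease: m(1 − f) / [1 − mf − (1 − m)g]

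For w = 0.7, m = 0.03, f = 0.2, g = 0.03:
- with disease, 0.0228/0.71053 = 3.21%;
- without disease, 0.024/0.9649 = 2.49%;
- ratio 1.29.

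Over w = 0.50-0.85, m = 1%-3% and g = 0-0.03, the false ratio is 1.09-1.22 at f = 0.1, 1.24-1.49 at f = 0.2 and 1.70-2.31 at f = 0.4. If f = g, both expressions reduce to m and the ratio is 1.00, so the direction depends on f exceeding g.

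*Illustration 3, the reverse flow.* A patient whose real CKD shows only in eGFR, and who dies with N17 coded, loses CKD status and falls from A to B. Suppose 10% of Group A qualifies by eGFR only and half of those decedents carry N17. Then 80 × 0.10 × 0.03 × 0.5 = 0.12 deaths move from A to B. That equals the 0.6 × 0.2 = 0.12 moving the other way at f = 0.2. The net shift is zero and the ratio returns to 1.00.

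**The case against.** The strongest reply has four parts.

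1. *The rule reaches few patients.* A reader might infer that the last eGFR by itself determines CKD and hence the group. It does not. N18, dialysis and the outpatient routes also give CKD, and cardiovascular disease, heart failure, hypertension or hyperlipidemia each place a patient in A or C regardless of eGFR. This stands and narrows the point. It does not remove it, because B and the D pool consist of exactly the patients with none of these.

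2. *The direction is not guaranteed.* A reader might infer that the bias always inflates Death in the diseased groups. Illustration 3 shows that N17 coding at death can cancel it, and survivors with a transient low value also offset it. What stands is a conditional direction.

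3. *The size is assumed.* This stands in full. Nothing in the documents supports any particular f, and no figure has been worked for C against D.

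4. *Little inference rests on Death.* The study is descriptive, the checklist marks hypotheses and measures of association as not applicable, and Death is one secondary row. SAP 10.1 plans tests among subgroups, including by underlying disease, but names none for Death by group. This stands and limits the importance. The row will still be read across the columns.

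**Conclusion.** The point holds in a limited form. For inpatients with no other qualifying disease and no other route to CKD, the grouping can depend on an eGFR from the stay in which they died, and Death is then tabulated by that grouping. The expected effect is Death overstated in A and C and understated in B and D, provided decedents are reclassified more often than survivors and N17 coding does not offset it.

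The ratio of 1.30 (80:20 split, 3% deaths in both groups, 20% of Group B decedents reclassified) and the other ratios above are illustrations, not estimates.

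Two stronger readings are not supported. One is that a higher death rate in Group A would be an artefact: the documents do not allow the built-in part to be separated from a real difference, in either direction. The other is that the primary outcome is compromised: on the inputs of Illustration 1 the Group A share moves only from 80.00% to between 80.12% and 80.30%, which is negligible. The change is worth making because it is cheap, not because the study's main result depends on it.

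**What to change.** For the Death rows of SAP Table 3, set group status by one rule for all inpatients, whatever their vital status, without using the eGFR of the latest stay. Count CKD from N18, from the outpatient routes, or from eGFR below 60 dated before the latest stay; the two values 90 days or more apart already required of outpatients would serve. State whether a dialysis prescription must also predate the latest stay. Show Death under the current last-eGFR rule beside it.

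The rule must not differ by vital status. Keeping the last value for survivors while taking an earlier one for decedents would let the outcome choose the measurement, which is the same fault in another form.

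The cost is a sentence each in Protocol 9.2.2 and SAP 6.3 and a second set of Death rows. Test date, discharge date and discharge way are already among the extracted variables (Protocol 9.3, Table 1). The downside is that some patients whose true CKD shows only in the latest stay's eGFR will count as non-CKD in those rows. How many is unknown, since the documents do not say how many inpatients have earlier results. The definition used for the primary proportions can stay as it is for this purpose.
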